10.0 DIRECT ACCESS TO SOURCE DATA/DOCUMENTS

The investigators, medical monitors, study monitor, study coordinator members of USAMMDA, members of the Institut Pasteur in Tunisia, Tunisian Minister of Health, and other government agencies Tunisian, and the U.S. Army Surgeon General's Human Subjects research Review Board as part of their duties, may access study data to monitor, audit, IRB review and pursue regulatory inspections of this trial's source data and documents as part of their responsibility to protect human subjects in research.

11.0 QUALITY CONTROL AND QUALITY ASSURANCE

USAMMDA will provide in-country quality control and quality assurance in accordance with good clinical practices.

12.0 ETHICS

The risks to normal volunteers associated with participation in this study are relatively low, whereas the potential benefit to society in the successful development of an effective topical treatment for cutaneous leishmaniasis skin is high. Therefore, on balance, the study stands on solid ethical basis.

The study will be explained to the subject/Legal Representative (LR) and to minors in a language that they can understand in order to assure that they are voluntarily cooperative and willing to participate in the protocol. Once the diagnosis of Cutaneous Leishmaniasis has been made (that is parasitologically proven to be Cutaneous Leishmaniasis), the investigator will obtain the subject's consent. The investigator will respond to all of the subject's questions and will continue to provide information after obtaining the subject's voluntary agreement. For the minors (≥15 years old but <18 years old), in addition to the LR-Consent form, an Assent (outlines the study in simplified language) will also be obtained. Any significant information that may affect the volunteer's health or willingness to continue participation that is found during the study will be made available to the volunteer/LR. Volunteers will be withdrawn from this research in the event of: (1)

the development of health conditions that would make the volunteer's continued participation in this study dangerous; or (2) the development of any other conditions which might occur that render the continued participation detrimental to the volunteer's health.

The conduct of this trial will follow the Helsinki Accords, FDA Good Clinical Practices, U.S. Army Surgeon General regulations concerning clinical trials and Tunisian Ministry of Health policies and regulations regarding clinical trials. Progress on this protocol will be provided to the Human Use Review Committees, the Study Monitors, the study coordinator, and USAMMDA annually and as appropriate during the study.

13.0 DATA HANDLING AND RECORDKEEPING

A copy of the protocol, CRF(s), other source documents and regulatory records will be kept on file by the U.S. Army Medical Research and Materiel Command for 2 years after the marketing application has been approved or if no application is to be filed or if the application was not approved for such indication for 2 years after the investigation was discontinued and the FDA is notified. As a co-sponsor, and according to Tunisian laws, copies of the protocol, CRF(s), other source documents and regulatory records will be kept by the Institut Pasteur in Tunis for 2 years after the marketing application has been approved or if no application is to be filed or for 15 years after the investigation is discontinued.

14.0 FINANCING

The financing of this trial is to come from the Tunisian Ministry of Health, Institut Pasteur Paris and U.S. Army Medical Materiel Development Activity (USAMMDA)

15.0 PUBLICATION POLICY

If journal articles are to be written then no volunteer will have their name or initials released, they will be identified by their volunteer number. Some of the photos may be used. It is anticipated that the results of this study will be presented to the scientific community via oral presentations at meetings and written publications in scientific journals.

16.0 VOLUNTEER REGISTRY DATA BASE REQUIREMENTS

It is the policy of the U. S. Army Medical Research and Materiel Command that data sheets (USAMRDC Form 60-R) are to be completed on all volunteers participating in research for entry into this Command's Volunteer Registry Database. The information to

be entered into this Subject confidential database includes your name, address, study number, study name, and dates. The intent of the database is two-fold: first, to readily answer questions concerning an individual's participation in research sponsored by USAMRMC; and second, to ensure that USAMRMC can exercise its obligation to ensure research volunteers are adequately warned (duty to warn) of risks and to provide new information as it becomes available. The information will be stored at USAMRMC for a minimum of 75 years. For The U.S. Army Medical Research and Materiel Command will go through the Institute Pasteur in Tunis to contact the subject if necessary, as the Tunisian law prohibits the release of Social Security Numbers.

17.0 ASSESSMENT OF SAFETY

17.1 Safety Parameters / Adverse Events

The recording of adverse events is the responsibility of the investigators. Volunteers will be instructed to contact the investigators immediately in the event they develop any unusual signs or symptoms post treatment. Follow-up information will be provided for all initial reports of serious and unexpected adverse events as described in 16.2, below.

17.1.1 Adverse Event

An adverse event temporally related to participation in the study should be documented, whether or not it is considered to be related to the test article. This definition includes intercurrent illnesses and injuries, or exacerbation of preexisting conditions. The following will be included in all IND safety reports: Subject identification number and initials; investigator's name and name of MTF; subject's date of birth, gender, and ethnicity; test article and dates of administration; signs/symptoms and severity; date of onset; date of resolution or death; relationship to the study drug; action taken; concomitant medication(s), including dose, route and duration of treatment, date of last dose.

17.1.2 Serious Adverse Event

A serious adverse event is any untoward medical occurrence that at any dose:

- * results in death
- * is life-threatening [Life threatening event is an event which presents the risk of death at the time of the event; it does not refer to an event which hypothetically might have caused death had it been more severe.]
- * requires inpatient hospitalization
- * results in persistent or significant disability/incapacity [Disabling/Incapacitating adverse event is any event, which may result in a substantial disruption of the volunteer's ability to carry out normal life functions. This definition is not intended to include minor cases of

headache, nausea, vomiting, diarrhea, influenza, rhinorrhea, lacrimation or accidental trauma, such as a sprained ankle.]

• Important medical events that may not result in death, may not be life-threatening or require hospitalization may be considered serious when, based on the medical judgement of the investigator, they may adversely affect the subject and may require medical/surgical intervention (i.e. an allergic reaction resulting in bronchospasm requiring immediate intervention without requiring hospitalization).

17.2 Recording and Reporting Adverse Events

17.2.1 Documenting Adverse Events

At the time of each visit all adverse events either observed or reported, will be documented in the CRF and in the subject's medical records. The investigator and clinical monitor team will evaluate each adverse event. In the event a medical diagnosis is made, the event will be reported as an AE or an SAE. If no medical diagnosis is made, individual data will be documented as the AE/SAE in the CRF. Details of any therapeutic measures taken in the event of AE/SAE will be recorded. Adverse events previously documented in the CRF will be recorded as 'ongoing', 'improved' or 'resolved' at subsequent visits. If an adverse event changes, or advances in quantity or quality, a new record of the event will be initiated.

17.2.2 Reporting Adverse Events

Reporting of serious and unexpected adverse events: All serious adverse events and all unexpected adverse events will be immediately reported to the Pharmacovigilance service of the Institut Pasteur of Tunis The information will be sent by facsimile to [name]. A written report will follow within 3 working days. In addition, serious and unexpected adverse experiences will be immediately reported by telephone to the Clinical Monitor [name] [name] to [contact], and the study Principal Investigator [name] [name] to [name] and the Study Coordinator [name] [contact]. The US Army MRMC Deputy for the Office of Research Protections will be also informed at [name]. Written follow-up information and the medical monitor's written review and assessment of the adverse event will be provided to the HSRRB and USAMMDA.

Unanticipated problems involving risk to subjects or others, serious adverse events related to participation in the study and all subject deaths should be promptly reported by [contact]), by email ([contact]), or by [contact]) to the Army Surgeon General's Human Subjects Research Review Board (HSRRB). A complete written report should follow the initial notification. In addition to the methods above, the complete report can be sent to the U.S. Army Medical Research and Materiel Command, ATTN: MCMR-ZB-P, [name]."

Routine reporting: will apply to local and non-serious systemic events.

17.2.3 Follow-Up of Adverse Events

The investigator will determine causality of the AE/SAE. This may include additional laboratory testing, follow up visits and/or histopathological examinations. All serious adverse events will be followed until resolution or SAE becomes stable. Non-serious adverse events will be followed until study conclusion. Reports relative to the subsequent course of an adverse event noted for any volunteer will be submitted to the local Medical Monitors.

17.3 Study Specific Definitions and Exceptions

Any hospitalization following initiation of the study for an elective procedure or therapy will be reported as a 'hospitalization (Not adverse event)' on the CRF. If this hospitalization is planned prior to study participation or arises from a pre-existing condition, it will be recorded on the medical history form and the CRF. For study specific definitions side effects and grades see Appendix A.

18.0 ROLES AND RESPONSIBILITIES OF THE STUDY PERSONEL

Principal Investigators: Responsible for protocol adherence and execution, passage of protocol through Tunisian protocol committee, tie-breaking blinded assessment of lesion changes in patients, data integrity, applying for and receiving approval for any modifications to the protocol or consent form in Tunisia, training of associate investigators, ensuring safety of the volunteers, and reporting of any adverse events.

Subinvestigators: Responsible for protocol adherence and execution, passage of protocol through Tunisian protocol committee, tie-breaking blinded assessment of lesion changes in patients, data integrity, applying for and receiving approval for any modifications to the protocol or consent form, ensuring safety of the volunteers, managing and reporting of any adverse events, briefing potential volunteers, obtaining proper informed consent, determining study eligibility based on screening data and the exclusion criteria, and recording all observations and data in the individual subject records.

Medical Monitors: Responsible to provide medical care and monitoring of research subjects for conditions that may arise during the conduct of the study. The medical monitor will review all serious adverse events and all unexpected adverse events (per ICH definitions) associated with the protocol and provide an unbiased written report of the event within 10 calendar days of the initial report. At a minimum, the medical monitor will comment on the outcomes of the adverse event (AE) and relationship of the AE to the test

article. The medical monitor will also indicate whether he/she concurs with the details of the report provided by the study investigator.

Coordinator Consultant and Study Monitor: Assures overall coordination of the study and protocol writing in collaboration with the PIs. Assures the study is conducted under cGCP in collaboration with the QC unit at USAMMDA. Uses his expertise in the product and previous experiences in Phase 1 and Phase 2 studies with WR 279,396 in support the Principal Investigators. Reviews weekly Reports and Summary Study Reports and communicates with the PIs accordingly. As a member of the Product Development Team keeps lines of communication open with the Product Managers and update other members of the Product Development Team in the United States by phone. Reviews and updates for the product managers the Annual Reports and Final reports.

Appendix A (Adverse or Unexpected Event Determination – Side Effects and Grades)

1. Cutaneous adverse reactions (i) on the edge of lesion (ii) on surrounding healthy skin [grade erythema separately from edema]

Grade 0: no reaction (no erythema or edema)

Grade 1: mild reaction (barely perceptible erythema or edema)

Grade 2: moderate reaction (well defined erythema or edema)

Grade 3: Severe reaction (very red erythema with raised > 2mm edema)

Grade 4: life threatening reaction (exfoliative dermatitis)

NOTE: Grade 3 reactions require immediate notification to Medical Monitor. Grade 4 reactions require immediate termination of treatment and ADVERSE EVENT NOTIFICATION.

2. Abnormal clinical laboratory values (DAIDS/NIH scale):

Parameter (units)	Grade 1	Grade 2	Grade 3	Grade 4
Creatinine (xULN)	>1-1.5	>1.5-3	>3-6	>6
AST/ALT (XULN)	1.25-2.5	>2.5-5	>5-10	>10
WBC (1,000/mm3)	1000-1500	750-999	500-749	< 500
PLT (1,000/mm3)	75-99	50-74	20-49	< 20
HGB (g/dL)	8-9.4	7-7.9	6.5-6.9	< 6.5

NOTE: Grade 2 require immediate notification to Medical Monitor.

Grade 3 and 4 reactions require immediate termination of treatment.

Grade 2, 3 and 4 laboratory values require evaluation of the volunteer. If the laboratory abnormality reflects clinically significant pathology, an ADVERSE EVENT report will be fill out and notification will occur.

3. Miscellaneous (associated with drug administration):

Pain:

Grade 0: none (feels no pain)

Grade 1: mild pain (does not interfere with daily activity)

Grade 2: moderate pain (interferes with daily activity)

Grade 3: severe pain (daily activities are interrupted)

NOTE: Grade 2 reactions require immediate notification to Medical Monitor. Grade 3 reactions require immediate termination of treatment and ADVERSE EVENT NOTIFICATION.

Vertigo:

Grade 0: none (feels no vertigo)

Grade 1: mild vertigo (does not interfere with daily activities)

Grade 2: moderate vertigo (interferes with daily activity)

Grade 3: severe vertigo (daily activities are interrupted)

NOTE: Grade 2 reactions require immediate notification to Medical Monitor. Grade 3 reactions require immediate termination of treatment and ADVERSE EVENT NOTIFICATION.

Tinnitus:

Grade 0: none (feels no ringing/buzzing/roaring etc.)

Grade 1: mild tinnitus (does not interfere with daily activities)

Grade 2: moderate tinnitus (interferes with daily activities)

Grade 3: severe tinnitus (daily activities are interrupted)

NOTE: Grade 2 reactions require immediate notification to Medical Monitor. Grade 3 reactions require immediate termination of treatment and ADVERSE EVENT NOTIFICATION.

Diminished hearing:

Grade 0: none (stays within normal limits) Normal = -10 db to 25 db

Grade 1: mild hearing loss (26 db - 40 db)

Grade 2: moderate hearing loss (41 db - 55 db)

Grade 3: severe hearing loss (56 db - 80 db)

Grade 4: profound hearing loss (> 80 db)

NOTE: Grade 2 reactions require immediate notification to Medical Monitor. Grade 3 and 4 reactions require immediate termination of treatment and ADVERSE EVENT NOTIFICATION.

4. Reporting of adverse events:

Serious and unexpected adverse experiences will be immediately reported to the Pharmacovigilance service of the Institut Pasteur of Tunis The information will be sent by facsimile to [name]. A written report will follow within 3 working days. In addition, serious and unexpected adverse experiences will be immediately reported by telephone to the Clinical Monitor [name] to [contact], and the study Principal Investigator [name] [name] to [name]. The US Army MRMC Deputy for the Office of Research Protections will be also informed at [name]. Written follow-up information and the medical monitor's written review and assessment of the adverse event will be provided to the HSRRB and USAMMDA.

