8.10 Determination of adverse reactions

8.10.1 Determination of side effects

On each day on which topical is administered, patients will be observed/questioned for the occurrence of the following local side effects (i) on the edge of lesion (ii) on surrounding healthy skin (Please see Case Report Form):

-pain by history (none, mild, moderate, or severe)

-erythema (none, mild=barely perceptible, moderate=well defined,

severe=very red)

-edema (none, mild=barely perceptible, moderate=well defined,

severe=raised >2mm; life threatening = exfoliative)

-vertigo (mild, moderate, or severe) -tinnitus (mild, moderate, or severe)

-diminished hearing (mild, moderate, severe or profound)

Subjective evaluation

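### Appendix A words skin Grade 3 as both signs together, against its own instruction to grade them separately and against section 8.10.1, so the immediate Medical Monitor alert may be applied inconsistently

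*Protocol*

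**What the plan says.** Item 1 of Appendix A grades skin reactions at the lesion edge and on surrounding healthy skin. Its heading instructs staff to "grade erythema separately from edema". Grades 0 to 2 offer the two signs as alternatives, for example "Grade 2: moderate reaction (well defined erythema or edema". Grade 3 changes the construction: "Grade 3: Severe reaction (very red erythema with raised > 2mm edema". The note below the scale says "NOTE: Grade 3 reactions require immediate notification to Medical Monitor", and requires termination of treatment at Grade 4. It attaches no action to Grades 1 and 2.

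Section 8.10.1, which governs the daily observation during treatment, gives each sign its own scale. For erythema it has "severe=very red", with no edema condition. For edema it has "severe=raised >2mm; life threatening = exfoliative", with no erythema condition.

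Section 17.3 sends the reader to Appendix A for the definitions and grades of side effects. Numbered grades, and the actions tied to them, are set out in Appendix A and not in 8.10.1.

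**The concern.** The line that sets the skin alert threshold disagrees with the heading above it, with the grades before it and with section 8.10.1. A grader who follows the heading and scores erythema alone finds no Grade 3 criterion for erythema alone; the same holds for edema. Because section 17.3 makes Appendix A the grading reference, staff are directed to the faulty line.

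What is at stake is one safety action. For skin, Grade 3 is the only grade below 4 to which the Appendix A note attaches any action. The other scales in the appendix alert earlier; for laboratory values the text is "NOTE: Grade 2 require immediate notification to Medical Monitor". Skin has no such lower threshold to catch a reaction graded one step too low.

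**Working it through.** No computed figure is involved. The check sets the texts side by side and follows each combination of signs through them.

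**Inputs**

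- Appendix A, item 1: the separate-grading heading, the wording of Grades 0 to 3, and the note on actions.
- Section 8.10.1: the separate erythema and edema scales.
- Section 17.3: Appendix A as the grading reference.

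**Step 1. Combinations of severe signs**

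| Erythema very red | Edema raised > 2 mm | Section 8.10.1 | Appendix A Grade 3 as worded |
|---|---|---|---|
| yes | yes | severe on both signs | met |
| yes | no | severe erythema | not clearly met |
| no | yes | severe edema | not clearly met |
| no | no | not severe | not met |

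Three combinations are severe under 8.10.1. The joint wording clearly covers 1 of the 3; the other 3 − 1 = 2 are left open.

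**Step 2. Where the open combinations go.** They do not fit Grade 2 exactly either, since that grade describes well-defined erythema or edema, which is the moderate level in 8.10.1. A grader must choose. One who relies on the heading or on 8.10.1 assigns Grade 3; one who insists on both signs assigns a lower grade, most naturally 2. The text permits either outcome.

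**Step 3. What follows from the choice.** Grade 3 brings immediate notification of the Medical Monitor; skin Grade 2 brings no action under the note. Trigger grades across Appendix A:

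| Scale | Lowest grade with immediate Medical Monitor notification |
|---|---|
| Skin reactions | 3 |
| Laboratory values | 2 |
| Pain | 2 |
| Vertigo | 2 |
| Tinnitus | 2 |
| Diminished hearing | 2 |

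Five of the six scales alert at Grade 2. Skin is the exception, so its Grade 3 wording carries more weight.

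**Step 4. Can one sign occur without the other?** The Protocol gives no rate, but its background suggests that the signs need not be reported together. Section 6.5.1 describes moderate to severe erythema in rats under twice-daily dosing and does not mention edema; it adds that once-daily dosing, the schedule used here, gave no clinical skin reaction. Section 6.5.2.1 reports 2 of 20 patients on a different paromomycin ointment with pruritus, tenderness and edema, without mentioning erythema. Neither report gives a frequency for this trial.

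**Step 5. Effect of the correction.** With *or* in place of *with*, all three severe combinations in Step 1 meet Grade 3, and Appendix A agrees with 8.10.1.

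**The case against.** The strongest reply is that the document resolves the ambiguity itself. The heading governs every grade beneath it, 8.10.1 defines severe for each sign, and Appendix A labels Grade 3 a severe reaction. A careful grader would read *with* as *or*. This stands as evidence of intent, and it makes the joint reading the weaker one. It does not remove the contradiction: a safety trigger should not depend on each grader overriding the wording of the designated reference.

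Three stronger readings are tempting, and the Protocol does not support them.

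- A reader might infer that a severe single sign is Grade 2 under the plan and so loses its alert. That is an inference: such a reaction fits neither line exactly, and the heading and 8.10.1 point to Grade 3. The supportable statement is that it may be graded below 3.
- A reader might infer that the Medical Monitor would never hear of the event. Section 17.2.1 has the investigator and clinical monitor team evaluate every adverse event, and section 17.2.3 sends reports on the later course of any adverse event to the Medical Monitors, whatever its grade. Section 17.2.2 gives local events routine reporting but requires immediate reporting of unexpected events. Section 6.5.5 lists erythema and edema as potential effects without stating severity, so whether a severe case counts as unexpected is left open. Patients are also observed on each treatment day, and Grade 2 pain has its own alert.
- A reader might infer that the tolerance comparison between the arms is compromised. Section 8.10.1 collects each sign on its own scale and refers to a Case Report Form that is not shown, which may already record them separately. Damage to the recorded data is not demonstrated.

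**Conclusion.** The wording contradiction is certain; its practical effect is limited. What is at risk is the immediacy and consistency of one notification, for reactions severe on a single sign. The effect arises only if at least one grader follows the joint wording instead of the heading or 8.10.1.

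The Protocol gives no rate for such reactions, and none is estimated here. Few are expected: section 6.5.4.2 reports only grade 1 local toxicity in the earlier study with occlusion and twice-daily application, and this trial applies the drug once daily.

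The termination rule at Grade 4, the withdrawal criteria in section 8.14, the sample size and the efficacy analysis are untouched. The point is a minor correction to safety wording, worth making because it concerns an alert threshold and the intended meaning is not in doubt.

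**What to change.** In Appendix A, item 1, replace the Grade 3 line with: *Grade 3: severe reaction (very red erythema, or edema raised > 2 mm)*. Leave the heading, the other grades and the note as they stand, so that either sign at the severe level triggers the notification already required. While making the change, confirm that the Case Report Form records erythema and edema separately, as 8.10.1 implies.

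The cost is one line of the appendix, processed as a protocol change under section 8.16, and possibly a few extra calls to the Medical Monitor.
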